### 5.3 Sample Size and Statistical Analysis Plan

We will enroll 30 subjects (15 male/15 female) in this pilot study. As part of clinical care, CHOP Radiology also performs approximately 4-5 contrast-enhanced ultrasound cases in a given day, which is higher in volume than any other children's hospital in the country.

---

A sample size of 30 should provide reasonable estimates of the perfusion metrics. For example, a sample size of 30 participants produces a two-sided 95% CI with a width equal to 0.3 when the estimated proportion is as small as 0.3 (95% CI=0.1, 0.5). Also, a two-sided 95% CI with a width equal 0.6 when the estimate of Pearson's product-moment correlation is 0.4 (95% CI= 0.05, 0.7).

Based on microangiopathy/ischemia observed in COVID-19 patients (9-11), we expect our cohort to display delayed perfusion, hypoperfusion or no perfusion of the myocardium, kidneys, and/or brain. Results of the myocardial, renal and brain perfusion will be assessed by two experienced researchers in the field of CEUS and report it qualitatively as either normal or abnormal. In case of diagnosis disagreement between the two raters, a third experienced researcher will confirm the correct diagnosis. Hence, the proportion and frequency of myocardial, renal, and/or brain perfusion abnormalities will be documented. As additional primary analysis, we will also assess quantitative CEUS and derive time-to-peak (TTP) and wash-in area under the curve (WiAUC).

Demographic characteristics and descriptive statistics (such as measures of frequency, central tendency, dispersion, and position) will be summarized for the sample and by male and female sex. The percentage of COVID-19 patients with an abnormal clinical exam will be computed. Time intensity curve analysis will provide further details on the nature of perfusion abnormalities. The following presents the variable names, output, and the reported statistics for the primary and secondary aims.

	Measured Variables	Output and statistics
Primary Analysis	Perfusion defect (hypo- or absent perfusion)	Proportion of COVID-19 patients with perfusion defect
Primary Analysis	Perfusion quantified using time-to-peak (TTP) and wash-in area under the curve (WiAUC) from the time-intensity curve of contrast signal	Summary statistics for TTP and WiAUC, for e.g. mean, standard deviation, 95% CI
Secondary Analysis	Clinical outcomes from chart review etc.	Correlation of CEUS metrics to clinical outcomes

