## 4 STUDY PROCEDURES

Screening will be performed via medical chart review and/or clinical referral of pediatric subjects at the Children's Hospital of Philadelphia. Subjects who fulfill eligibility criteria will be included.

CEUS scan will be performed by CHOP study team members and/or dedicated research ultrasonographers. Subjects will undergo one CEUS exam. The dosing plan will be weight-adjusted, based on a dose of 0.03 mL/kg. Up to two injections per study will be performed as per product label/FDA guidelines. Subjects' and personnel safety will be handled according to clinical protocol for COVID-19.

Organ perfusion will be evaluated in the heart, kidneys and/or brain, provided there is evidence of cardiovascular compromise, myocardial injury, acute kidney injury, and new-onset neurological symptoms. Brain ultrasound will occur if there are new-onset neurological symptoms. We will use a low energy approach to minimize the risk of thermal injury or disruption of the blood-brain-barrier (mechanical index < 0.2 is safe).

Analysis of CEUS imaging by the Principal Investigator will be performed, in addition to medical chart review for clinical outcomes (exploratory analysis).

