### 5.2 Secondary Endpoints

1. Evaluate heart, kidneys and/or brain perfusion using time to peak (TTP) and wash-in area under the curve (WiAUC).
2. Death within 28 days of imaging or mechanical ventilation within 14 days of imaging as reported in the medical chart.
3. Myocardial infarction, stroke, or renal failure as reported in the medical chart.

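### Section 5.3's two precision examples print widths that do not match their limits and name no interval method, and the plan gives no suitable measure for perfusion defect against yes/no outcomes

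*Combined protocol and SAP*

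**What the plan says.** Section 5.3 plans 30 children and gives two illustrations of precision, both at n = 30. They are the only quantitative support for that number.

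- Proportion: the sample "produces a two-sided 95% CI with a width equal to 0.3 when the estimated proportion is as small as 0.3 (95% CI=0.1, 0.5".
- Correlation: "width equal 0.6 when the estimate of Pearson's product-moment correlation is 0.4 (95% CI= 0.05, 0.7".

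Neither example names an interval method. Section 1.1 promises 95% intervals for means and proportions, also without a method.

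On the clinical outcomes, Section 5.2 lists "Death within 28 days of imaging or mechanical ventilation within 14 days of imaging as reported in the medical chart" and "Myocardial infarction, stroke, or renal failure as reported in the medical chart". Section 3.1 names the same five events and calls the analysis exploratory. The secondary row of the Section 5.3 table gives the statistic as "Correlation of CEUS metrics to clinical outcomes".

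On denominators, the primary endpoint in Section 5.1 counts patients. Section 5.3 adds that "the proportion and frequency of myocardial, renal, and/or brain perfusion abnormalities will be documented". Section 4 states: "Brain ultrasound will occur if there are new-onset neurological symptoms".

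**The concern.** Each precision example contradicts itself on its face. A reader cannot tell whether the width or the limits are meant, nor which method produced them or will be used in the analysis. An inconsistent justification of n is worth correcting even in a pilot.

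The second question is whether a Pearson example tells the reader anything about the planned outcome analysis. The named outcomes are events that happen or do not. One CEUS result, perfusion defect, is also yes/no, so that comparison is a two-by-two table. The information in such a table depends on how many children have the event, which an interval for r at n = 30 does not show.

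**Working it through.** **Inputs.** From Section 5.3: n = 30, two-sided 95%, proportion 0.3 (9/30), r = 0.4, and the printed widths and limits. The documents give no event counts and no numbers imaged per organ. Those used in steps 4 to 6 are assumptions.

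**1. Printed figures.** 0.5 − 0.1 = 0.4, against a printed width of 0.3. 0.7 − 0.05 = 0.65, against a printed width of 0.6.

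**2. Reproducing the plan's figures.**

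- Wald: 0.3 ± 1.96 × √(0.3 × 0.7/30) = 0.3 ± 0.164, which is 0.136 to 0.464, width 0.328. At one decimal this is 0.1, 0.5 and 0.3, as printed.
- Clopper-Pearson, 9/30: 0.147 to 0.494, width 0.347. This also rounds to 0.1, 0.5 and 0.3.
- Wilson, 9/30: 0.167 to 0.479, width 0.312. The lower limit rounds to 0.2, so this is not the source.
- Fisher z: atanh(0.4) = 0.4236 and 1.96/√27 = 0.3772. The limits are tanh(0.0465) = 0.046 and tanh(0.8008) = 0.665, width 0.618. This rounds to 0.05 (two decimals), 0.7 and 0.6 (one decimal), as printed.

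Both examples therefore reproduce. The mismatch is separate rounding, and two methods fit the first example equally well.

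**3. Widest case and number of decimals.** A proportion of 0.3 does not give the widest interval. At 15/30 the exact interval is 0.313 to 0.687, width 0.374. Two-decimal limits would recreate the mismatch: 0.15 to 0.49 spans 0.34 (width 0.35), 0.31 to 0.69 spans 0.38 (width 0.37), and 0.05 to 0.66 spans 0.61 (width 0.62). Three-decimal limits do not: 0.494 − 0.147 = 0.347, 0.687 − 0.313 = 0.374 and 0.665 − 0.046 = 0.619, which round to 0.35, 0.37 and 0.62.

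**4. TTP and WiAUC (time to peak, wash-in area) against a yes/no event.** Pearson's r is here the point-biserial correlation. In simulation its Fisher-z interval covered about 93 to 97%, so it is usable. It does not display the dependence on event counts. The half-width of a mean difference in SD units, t(0.975, 28) × √(1/n₁ + 1/n₂) with t = 2.048, does:

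- 15 events of 30: 2.048 × 0.365 = 0.75 SD
- 6 events: 2.048 × 0.456 = 0.93 SD
- 3 events: 2.048 × 0.609 = 1.25 SD

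For r = 0.4, Fisher z gives 0.046 to 0.665 in all three cases.

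**5. Perfusion defect against a yes/no event.** Assume 9 children with a defect and 21 without, with events in 4/9 and 2/21. Then r = (4 × 19 − 5 × 2)/√(9 × 21 × 6 × 24) = 66/165.0 = 0.40. Fisher z again returns 0.046 to 0.665. The risk difference is 0.444 − 0.095 = 0.349, with a Newcombe score interval of 0.028 to 0.646, in units a later trial could use. In simulation, coverage of the Fisher-z interval fell to about 88% in several assumed sparse scenarios. One of them (30 children, defect in 30%, event risk 0.4 with and 0.1 without a defect) gave 0.888 over 200,000 tables, leaving out tables in which r is undefined.

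**6. Organ-specific estimates.** If only 20 children are imaged for an organ, the exact interval at 0.30 is 0.119 to 0.543 (width 0.42), and the interval for r = 0.4 is −0.052 to 0.716 (width 0.77). With 10 imaged, they are 0.067 to 0.652 (0.59) and −0.307 to 0.822 (1.13).

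**The case against.** The strongest reply is that nothing was miscalculated. Every printed figure is a correct rounding of a standard interval, and the printed limits suggest a wider interval than the printed width does, so nobody is clearly led towards false precision. That stands. A reader might infer that the sample-size calculation is wrong or that 30 is too few; step 2 shows otherwise.

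A reader might also infer that someone planning the next trial would be misled, because Section 1.1 ties 95% intervals to that trial's design. Those are the intervals the pilot will observe, not the illustration in Section 5.3, so the documents do not support this.

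On organ denominators, a reader might infer that 30 is wrong for the primary estimate. It is not shown to be. The endpoint is per patient, and inclusion criterion 4 (Section 3.3.1) requires at least one organ-related indication in every child. Only the brain has its own explicit imaging condition. The general sentence, "Organ perfusion will be evaluated in the heart, kidneys and/or brain, provided there is evidence of cardiovascular compromise", goes on to list the indications jointly and is ambiguous, and Section 3.1 has the organs examined at the same time. Organ-level numbers may be below 30; the text goes no further.

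On the outcomes, it would be too strong to say that Pearson's r cannot be used with a yes/no variable. For TTP and WiAUC it is valid. Section 4.4.1 also collects non-binary chart variables such as hospital stay and time to recovery, so a continuous example is not out of place. What remains is the two-by-two comparison, where the Fisher-z interval can fall short and no other measure is named.

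**Conclusion.** The point holds as a minor one. As printed, the two examples conflict with themselves by 0.1 (0.4 against 0.3) and 0.05 (0.65 against 0.6), because limits and widths were rounded separately and no method is named. The unrounded widths are 0.33 (Wald) or 0.35 (exact) and 0.62, so the stated precision becomes slightly less favourable. These figures rest only on the plan's own inputs.

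For perfusion defect against a yes/no outcome, the plan needs a measure other than a correlation interval. The coverage figure behind this depends on assumed defect and event rates. The analysis is exploratory, so the consequence is limited.

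The organ-level denominator is a reporting note only. Nothing here changes n = 30 or the primary endpoint.

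**What to change.** Replace the two examples in Section 5.3 with text such as:

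> With n = 30 and an estimate of 0.30, the exact (Clopper-Pearson) 95% CI is 0.147 to 0.494 (width 0.35); at 0.50 it is 0.313 to 0.687 (width 0.37). For r = 0.40 the Fisher-z 95% CI is 0.046 to 0.665 (width 0.62).

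Another named method, such as Wilson, is equally acceptable if the analysis uses it too.

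In the secondary analysis:

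- For perfusion defect against each yes/no outcome, report the risk difference with a score or exact 95% CI and the event counts, instead of a correlation interval.
- For TTP and WiAUC, the point-biserial r may stay. A mean difference between children with and without the event, with its 95% CI, may be added because it is easier to interpret.
- Give the number of children imaged with every organ-specific estimate.

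The cost is a few lines of SAP wording and one simple comparison per outcome. No extra patients or data are needed.

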### PROTOCOL SYNOPSIS

---

Study Title	Contrast Enhanced Ultrasound (CEUS) Detection of Microvascular Perfusion Impairment in COVID-19 Pediatric Patients
Funder	Children's Hospital of Philadelphia
Clinical Phase	Pilot study.
Study Rationale	Initial data from COVID-19 patients in China and Italy suggests that one of the primary causes of death is significant endothelial injury leading to blood clotting and impaired multiorgan microvascular perfusion. This pilot study uses a safe, convenient bedside imaging tool called contrast-enhanced ultrasound (CEUS) to estimate the extent of microvascular perfusion impairment in the heart, kidneys and brain of COVID-19 pediatric patients and assess the significance of imaging findings by correlating to clinical outcomes.
Study objectives	
Primary: Assess microvascular perfusion of the heart, kidneys and/or brain using CEUS in patients with confirmed or probable diagnosis of COVID-19.
 
Secondary: Correlate CEUS measures of microvascular perfusion of the heart, kidneys and/or brain to clinical outcomes.

Test Article(s) (If Applicable)	Sulfur hexafluoride lipid-type A microspheres (Lumason™, Bracco Inc) is an FDA-approved ultrasound contrast agent which consists of active ingredients including Sulfur hexafluoride (strength 60.7 mg in 1 mg), Distearoylphosphatidylcholine, DL- (strength 0.19 mg in 1 mg), 1,2-Dipalmitoyl-Sn-Glycero-3-Phospho-(1'-Rac- Glycerol), Sodium Salt (0.19 mg in 1 mg). Inactive ingredients include Polyethylene Glycol 4000 (strength 24.56 mg in 1 mg) and Palmitic Acid (0.04 mg in 1 mg). The Sulfur hexafluoride lipid microspheres are composed of SF 6 (molecular weight 145.9) gas in the core surrounded by an outer shell monolayer of phospholipids consisting of 1,2-Distearoyl-sn-glycero-3-phosphocholine (DSPC) and 1,2-Dipalmitoyl-sn-glycero-3-phosphoglycerol, sodium salt (DPPG-Na) with palmitic acid as stabilizer. Sulfur hexafluoride lipid-type A microspheres fall under Category B, that is, animal reproduction studies have failed to demonstrate a risk to the fetus and there are no adequate and well-controlled studies in pregnant women. 1,2-Distearoyl-sn-glycero-3-phosphocholine (DSPC), with empirical formula C 44 H 88 NO 8 P, has a molecular weight of 790.6. 1,2-Dipalmitoyl-sn-glycero-3-phospho-rac-glycerol sodium (DPPG-Na),

---

---

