### Contrast-Enhanced Ultrasound (CEUS) for Microvascular Flow Assessment

[figure not shown]
CEUS uses intravascularly injected microbubbles of 2-3  $\mu\text{m}$  in size, smaller than red blood cells, to depict perfusion abnormalities down to 10  $\mu\text{m}$  resolution. Organ perfusion abnormalities including focal or diffuse infarct can readily be detected with CEUS but not with Doppler ultrasound. It is FDA-approved for pediatric and adult applications for the evaluation of the heart and liver and used clinically at CHOP. CEUS has previously been used to evaluate cardiac/renal microvascular perfusion (23-28).

The PI has pioneered the application of CEUS in the pediatric population (29-34) and is conducting two Investigational New Drug-approved clinical trials in the most vulnerable patients including critically ill, unstable infants with hypoxic ischemic injury and necrotizing enterocolitis. CEUS can be performed conveniently at bedside without the need for patient transport, it is easily repeatable, and cost-effective, which are critical aspects of resource allocation during the COVID-19 pandemic. Furthermore, there is no current technology that can accurately assess organ microvascular perfusion. Color Doppler, also performed at the bedside, is limited to macrovascular flow (Figure 2).

[figure not shown]
**Figure 2.** Doppler versus CEUS Assessment of Brain Microvascular Flow. Shown are Doppler (A) and CEUS (B) images of the porcine brain in coronal plane demonstrating the lack of microvessels depicted with Doppler as compared to delineation of  $< 10 \mu\text{m}$  microbubbles throughout the brain on CEUS.

CEUS images can be assessed in different ways. The degree of perfusion defect can be categorized as mild, moderate, or severe. Advanced quantitative analysis of perfusion can be done either by intensity analysis or microbubble tracking methods. (Figure 3).

**Figure 3.** Shown to the left is a post-processed CEUS image of the same porcine brain depicting microvasculature down to the  $< 10 \mu\text{m}$  resolution. Microvascular flow trajectory and velocity can also be calculated from this data.

Even upon visual examination, organ ischemia is readily evident on CEUS, whereas it is difficult to assess with grayscale or Doppler ultrasound alone (Figure 4). At CHOP, CEUS is routinely done as part of clinical practice, and up to 4-5 CEUS exams are performed per day.

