## 3.3 Study Population

### 3.3.1 Inclusion criteria

1. Patient (male/female) hospitalized at CHOP.
2. Patient 17 years of age or younger.
3. Diagnosis of COVID-19 or high clinical suspicion for COVID-19 despite negative tests (according to the definition of probable case by the ECDC).
4. Patient has evidence of cardiovascular compromise, myocardial injury, acute kidney injury, and/or new-onset neurological symptoms).
5. Parental/guardian permission (informed consent)

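### The visual CEUS read is recorded only as normal or abnormal, although the protocol names a severity scale and aims at extent; adding the grade is a cheap improvement for the exploratory analyses

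*Combined protocol and SAP*

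**What the plan says.** Section 5.3 (Sample Size and Statistical Analysis Plan) has two readers assess myocardial, renal and brain perfusion and "report it qualitatively as either normal or abnormal", with a third reader settling disagreements. The analysis table in the same section defines the primary variable as a perfusion defect and puts reduced and absent perfusion into that one category.

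The background on CEUS in section 1.1 describes a finer scale: "The degree of perfusion defect can be categorized as mild, moderate, or severe". The Study Rationale in the synopsis gives the purpose as "to estimate the extent of microvascular perfusion impairment in the heart, kidneys and brain of COVID-19 pediatric patients". No endpoint in sections 5.1 or 5.2, and no row of the 5.3 table, uses a grade.

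On what the reads may show, section 5.3 says "we expect our cohort to display delayed perfusion, hypoperfusion or no perfusion of the myocardium, kidneys, and/or brain", and section 3.3.1 restricts entry: "Patient has evidence of cardiovascular compromise, myocardial injury, acute kidney injury, and/or new-onset neurological symptoms". No expected proportion abnormal is stated.

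The plan also derives two continuous time-intensity parameters, TTP and WiAUC. Section 5.3 calls them an additional primary analysis; section 5.2 lists them as secondary. The secondary analysis correlates CEUS metrics in general with clinical outcomes, and section 3.1 labels that correlation exploratory.

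**The concern.** Under the 5.3 rule, a small patchy defect and an unperfused kidney receive the same value, so the visual read cannot describe extent beyond presence or absence in each organ.

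It may also become a weak variable to relate to outcome. Every child enters with evidence of organ compromise, and the plan expects disturbed perfusion. Section 5.1 classes a child by any hypoperfused area in the organs imaged, which pushes the patient-level share up. As an illustration only, with an assumed 50% rate per organ and independence, two organs give 1 − 0.5² = 75% and three give 1 − 0.5³ = 87.5%. If most reads are abnormal, a two-level variable has few values on one side.

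At stake are the usefulness of the visual read in the exploratory correlation and the descriptive material this pilot is meant to hand to a later trial, namely the distribution of grades and the readers' agreement on them.

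**Working it through.** **Inputs from section 5.3.** The sample size: "We will enroll 30 subjects (15 male/15 female) in this pilot study". Precision for a proportion: "two-sided 95% CI with a width equal to 0.3 when the estimated proportion is as small as 0.3 (95% CI=0.1, 0.5". Precision for a correlation: "width equal 0.6 when the estimate of Pearson's product-moment correlation is 0.4 (95% CI= 0.05, 0.7".

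**The plan's own figures.**
- Proportion: 0.3 ± 1.96 × √(0.3 × 0.7 / 30) gives 0.136 to 0.464, width 0.33.
- Correlation (Fisher z, standard error 1/√27): r = 0.4 gives 0.046 to 0.665, width 0.62.

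Both agree with the plan after rounding. Neither depends on whether a grade is recorded.

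**Assumptions for the comparison (not in the documents).** Severity lies on a standard normal scale, and a fraction p of reads falls above the cut for abnormal. Reading is free of error. Grades are scored 0 to 3, and in the base case the abnormal reads split equally into mild, moderate and severe.

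**Information kept.** This is the squared correlation between the underlying scale and the recorded value, with φ the standard normal density.
- Yes/no: φ(c)² / [p(1 − p)], where c cuts off the upper fraction p.
- Four grades: [φ(c₁) + φ(c₂) + φ(c₃)]² / Var(score), with cuts at the three grade boundaries.

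Yes/no:
- p = 0.3: 0.3477² / 0.21 = 0.58
- p = 0.5: 0.3989² / 0.25 = 0.64
- p = 0.8: 0.2800² / 0.16 = 0.49
- p = 0.9: 0.1755² / 0.09 = 0.34

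Four grades, equal thirds:
- p = 0.3: (0.3477 + 0.2800 + 0.1755)² / 1.04 = 0.62
- p = 0.5: (0.3989 + 0.3636 + 0.2498)² / 1.333 = 0.77
- p = 0.8: (0.2800 + 0.3975 + 0.3286)² / 1.173 = 0.86
- p = 0.9: (0.1755 + 0.3863 + 0.3477)² / 0.96 = 0.86

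The split of grades matters somewhat. If 70% of abnormal reads are mild, 20% moderate and 10% severe, the four-grade share is 0.76 at p = 0.5, 0.82 at 0.8 and 0.78 at 0.9. Other splits and scorings reach about 0.64 at p = 0.3 and 0.87 at 0.8.

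**What this means with 30 children.** Take the plan's example correlation of 0.40 as the true correlation on the underlying scale. The recorded correlation is 0.40 × √(share). Power is the approximate two-sided 5% power from Fisher z, with equal thirds.

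| Abnormal | Normal reads expected of 30 | r, yes/no | r, four grades | Power, yes/no | Power, four grades |
|---|---|---|---|---|---|
| 30% | 21 | 0.30 | 0.31 | 37% | 39% |
| 50% | 15 | 0.32 | 0.35 | 41% | 48% |
| 80% | 6 | 0.28 | 0.37 | 32% | 53% |
| 90% | 3 | 0.23 | 0.37 | 24% | 53% |

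An uncategorised continuous measure with the same true correlation would have about 60%.

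As a cross-check on the yes/no read, assume outcome rates of 10% with a normal read and 50% with an abnormal one. Exact Fisher power is then 54% with 15 normal reads, 24% with 6 and 2% with 3.

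**The case against.** The case for leaving the plan alone is substantial.

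- **The primary endpoint needs only a yes/no read.** Section 5.1 is a proportion, normal against hypoperfused. This stands in full.
- **The outcome analysis does not rest on the visual read.** TTP and WiAUC are continuous and fall under the metrics to be correlated, and the plan's precision example is a Pearson correlation. This stands. They do not fully replace a grade: section 1.1 derives them from a region of interest, and 5.3 gives no rule for placing it, so they need not show how much of an organ is affected.
- **A high abnormal share is inferred.** A reader might conclude that the cohort will be nearly all abnormal, so that the main read has almost no variation left and cannot be related to outcome. The documents do not support that. The only figure, 0.3, is a precision example and not a prediction, and there grading adds almost nothing. Section 8.3.3 mentions a high proportion only as a potential finding. Clinical compromise at entry does not guarantee a visible defect.
- **Reads are by organ.** Rates for single organs can be lower than the patient-level rate, and the number of affected organs can itself vary.
- **The severity scale is background.** Section 1.1 offers it as one of several ways to assess images, so choosing a yes/no read plus quantification is not a contradiction.
- **Images are archived** (section 8.1), so grades could be read later. This lowers the urgency, but a later reading would not be prespecified and might be made with outcomes known.
- **Grading needs more than a form field.** No criteria for the grades exist, and the third-reader rule is written for a two-way diagnosis. Both need short additions.

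**Conclusion.** The point holds as a cheap improvement. The plan drops a severity grade that the protocol itself describes, in a study meant to estimate extent. The loss falls only on the visual read's description of extent and on its use in an exploratory correlation; the primary proportion is unaffected.

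The loss is negligible if about 30% of reads are abnormal, moderate at 50%, and large only at about 80% or more. These sizes rest on the assumed normal severity scale, the split of grades and error-free reading. Disagreement between readers would shrink the gain.

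The stronger inference, that the read will be nearly constant or cannot be correlated with outcome, is not established: no abnormal proportion is predicted, and TTP and WiAUC are available for the same analysis. Nor would grading make the correlation well powered. Under the assumptions above it reaches about 39% to 53% with 30 children.

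**What to change.** In section 5.3:

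1. Have the same two readers also record none, mild, moderate or severe for each organ imaged, independently and at the same read, using brief written criteria for each grade.
2. Keep the primary proportion as it is, counting any grade above none as abnormal.
3. In the exploratory outcome correlation, use the ordinal grade with a rank-based method, alongside TTP and WiAUC.
4. Report weighted kappa from the two independent grades, before any disagreement is resolved.
5. Extend the third-reader rule to grades, for example by taking the median of the three grades when the first two differ.

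The cost is one extra field per organ on the reading form, with the same readers and sitting, plus short grading criteria to write. Disagreements will be more frequent than with a two-way read, so the third reader will be called on more often. Sample size, imaging and the primary analysis do not change.

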**Figure 3.** CEUS of the kidneys. Shown are sagittal CEUS images of the kidneys, (A) demonstrating homogeneous perfusion of normal right kidney with high signal due to intravascular microbubbles and (B) demonstrating low signal regions (yellow arrows) consistent with ischemia.

**CEUS Quantification:** It should be noted that CEUS gives a wide range of quantifiable, continuous parameters reflective of tissue perfusion. Injection of contrast results in increased acoustic signal quantifiable as signal intensity in decibels (dB). Spatiotemporal changes in signal intensity are then measured to reflect tissue perfusion, flow rate, blood volume, and many other parameters that can be derived from the *time intensity curve (TIC)* analysis. In TIC analysis, signal intensity in a given region of interest is plotted over time and parameters are extracted from the curve (for e.g. time to peak or TTP, wash-in area under the curve or WiAUC, rise time or RT, wash-in rate or WiR, wash-in perfusion index or WiPi). This is a well-accepted conventional approach to CEUS quantification previously used by the PI in the report of the first clinical guidelines for application of brain CEUS in infants (29), quantitative detection of hypoxic ischemic injury using brain CEUS (30), and quantification of tumor microvessel density (35). More advanced analysis involves the particle tracking method, in which individual intravascular microbubbles are tracked across thousands of ultrasound frames to quantify microbubble velocity, spatial distribution, trajectory (and other sophisticated parameters such as shear stress, acceleration-deceleration, etc.) (36). The conventional time intensity curve and particle tracking method combined would yield more than >30 continuous CEUS microvascular perfusion parameters that can each, or in combination, be correlated to clinical outcomes in this proposal.

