### 3.3.2 Exclusion Criteria

1. Medical history of Lumason hypersensitivity.

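### Section 5.3 pools TTP and WiAUC over all ages up to 17 and correlates CEUS metrics with outcome unadjusted; age, though available, has no role in either analysis

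*Combined protocol and SAP*

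**What the plan says.** - **Who is enrolled.** Section 3.3.1 requires "Patient 17 years of age or younger" and sets no lower limit. The one exclusion in Section 3.3.2 is "Medical history of Lumason hypersensitivity". Section 5.3 states "We will enroll 30 subjects (15 male/15 female) in this pilot study".
- **Perfusion metrics.** The analysis table in Section 5.3 asks for "Summary statistics for TTP and WiAUC, for e.g. mean, standard deviation, 95% CI" and labels this a primary analysis. The row names no breakdown. The only breakdown in the section is in the sentence on demographic and descriptive statistics, which "will be summarized for the sample and by male and female sex".
- **Link to outcome.** The secondary row reads "Correlation of CEUS metrics to clinical outcomes", with no covariate, stratum or model. Sections 1.1, 3.1 and 4 call this analysis exploratory.
- **Age data.** Section 4.4.1 collects date of birth. Section 5 gives age no role in the perfusion or correlation analyses.
- **Purpose.** Section 1.1 says the descriptive statistics from this pilot are to feed the design of a later trial.

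**The concern.** TTP is a time and WiAUC an integrated signal. It is reasonable to expect both to depend on circulation time, body size and imaging depth, and brain curves on the skull window. All of these change between infancy and 17 years. The risk of ventilation, renal failure or death may also differ by age. This is general reasoning; the documents report no such relation.

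If both relations exist, two outputs suffer:

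- **The crude correlation** cannot separate an effect of perfusion on prognosis from children of different ages having both different curves and different risk. The bias can run in either direction.
- **The pooled SD** contains age variation as well as variation from disease and measurement. A later trial that adjusts for age, or enrols a narrower age range, would be planned on the wrong SD.

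**Working it through.** **Inputs from the documents (Section 5.3):** n = 30; planning correlation r = 0.4 with 95% CI 0.05 to 0.7, width 0.6.

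**Assumptions (the documents give no values):** a = correlation of age with the CEUS metric; b = correlation of age with the outcome; event rates of 10% and 30%.

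**1. The plan's own figure.** Fisher z: tanh(atanh(0.4) ± 1.96/√(30 − 3)) = 0.046 to 0.665, width 0.618. This agrees with the printed figures after rounding.

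**2. Correlation produced by age alone.** With no CEUS–outcome link at a given age, the crude r is a × b. At n = 30 the two-sided 5% critical value is |r| = 0.361.

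- 0.3 × 0.3 = 0.09
- 0.5 × 0.5 = 0.25
- 0.7 × 0.5 = 0.35

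**3. How often that looks like a finding.** I simulated samples of 30 with normal variables and no true link, using a two-sided 5% test. For the binary columns, b applies to a latent risk that is then cut at the event rate.

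| a / b | Continuous outcome, crude | Binary, 30% events, crude | Binary, 10% events, crude | Age-adjusted, all three |
|---|---|---|---|---|
| 0.3 / 0.3 | 8% | 7% | 6% | about 5% |
| 0.5 / 0.5 | 27% | 17% | 12% | about 5% |
| 0.7 / 0.5 | 49% | 30% | 19% | about 5% |

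Runs with other seeds differ by about one percentage point. Using ranks instead of raw values, the adjusted rates were 4–5%.

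**4. Masking.** If the correlation at a given age is 0.4 and the age effects oppose each other, the crude r is 0.4 × √((1 − a²)(1 − b²)) − ab, with b taken as its absolute size.

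- 0.3 / −0.3: 0.4 × 0.91 − 0.09 = 0.27
- 0.5 / −0.5: 0.4 × 0.75 − 0.25 = 0.05

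**5. Pooled SD.** Removing a linear age term multiplies the SD by √(1 − a²): 0.95, 0.87 and 0.71 for a = 0.3, 0.5 and 0.7.

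**6. Price of adjustment.** With one covariate the standard error on the z scale is 1/√(n − 4) instead of 1/√(n − 3). For r = 0.4:

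- n = 30: 0.039 to 0.669, width 0.629, against 0.618 crude.
- If an organ were imaged in only 15 children (an assumption): width 0.93 against 0.90.
- If in only 10 (an assumption): width 1.20 against 1.13.

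At a 10% event rate, 0.9^30 = 4% of studies of 30 would contain no event, so no correlation could be computed.

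**The case against.** **Every age correlation is assumed.** This stands. At 0.3/0.3 the harm is close to nil. Substantial distortion needs links of about 0.5 or more. A reader might infer that the planned correlation is in fact confounded by age; the documents show only that the analysis could not tell.

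**The outcomes are mostly yes/no.** This stands. Section 5.2 names death, ventilation, infarction, stroke and renal failure, for which the false-positive rates are well below the continuous-outcome ones. The continuous case is not irrelevant, because Section 4.4.1 also collects hospital stay and time to recovery, but it is the upper end.

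**The correlation is exploratory, in a pilot of 30, and no test is specified.** This limits the weight. The primary endpoint in Section 5.1, a reader-judged proportion, does not use the correlation. It does not remove the point: the TTP and WiAUC summaries are labelled primary in Section 5.3, and the statistics are meant to inform a later trial. The false-positive rates can be read as the chance that a 95% interval wrongly excludes zero.

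**Age is not ignored altogether.** Correct. A demographic summary would ordinarily include it, so the gap is confined to the perfusion and correlation analyses. Likewise, newborn enrolment is only inferred from the missing lower limit. The weight-scaled injected volume may offset part of any body-size effect on WiAUC.

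**Adjustment may fail in small cells.** This stands. Section 4 makes imaging depend on organ findings, and the brain is scanned only for new neurological symptoms. Because the plan cites "the first clinical guidelines for application of brain CEUS in infants", a reader might infer that separate infant brain results must be required. The documents do not support that as a requirement: the group could be one or two children. Nor do they support replacing the crude analysis with the adjusted one.

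**Conclusion.** The omission is plain in the text: pooled TTP and WiAUC over an open-ended paediatric age range, sex as the only named breakdown, and an unadjusted correlation with outcome, although age is available.

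The consequence is conditional. Under assumed age links of 0.5/0.5 to 0.7/0.5 and no true effect, the chance of a spurious correlation is about 27–49% for a continuous outcome and 12–30% for a binary one with 10–30% events, against a nominal 5%. Under 0.3/0.3 it is 6–8%. Opposing links of 0.5 could reduce a real 0.4 to 0.05. These figures rest on normal variables, linear age effects and, for binary outcomes, a latent-risk model.

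This is a modest gap, worth closing because closing it costs almost nothing. It is not a flaw in the primary endpoint.

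**What to change.** In Section 5.3 add:

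1. For each organ, plots of TTP and WiAUC against age, with the SD after removing a linear age term reported beside the pooled SD.
2. Beside each crude CEUS–outcome correlation, a partial rank correlation with age as the only covariate. Label it exploratory and report it where the number of children imaged and the event count allow. State the minimum numbers in advance.

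Tables by age band and organ, and brain results for infants alone, are optional and may be too sparse to read.

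**Cost.** Wording in the analysis plan; no new data. One degree of freedom, which widens the interval for r = 0.4 at n = 30 from about 0.62 to 0.63. The loss is greater for organs imaged in few children and for rare events, where the adjusted estimate may have to be omitted.
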